8.1.1.2.3 Non-Serious Adverse Events other than Adverse Events of Special Interest

All non-serious AEs (in addition to AESI) must be collected according to the appropriate level of MedDRA classification.

8.1.1.3 Serious Health Threat (Immediately Reportable to the MAH)

A serious health threat is defined as a signal from any AE that indicates an imminent risk of death or a serious deterioration in the health of patients, users, or other persons, and that requires prompt remedial action for other patients, users, or other persons. A serious health threat is required to be reported by the treating physician to the MAH

immediately (i.e., no more than 24 hours after learning of the event) are described in [Section 8.1.3.1](#).

8.1.1.4 Exemption of Specific Adverse Events from Collection

Not applicable for this study.

8.1.2 Methods and Timing for Capturing and Assessing Safety Parameters

The physician is accountable for ensuring that all AEs collected as per protocol (see [Section 8.1.1.1](#) for definition) are recorded in the AE section of the eCRF and reported to the MAH in accordance with instructions provided in this section and in [Section 8.1.3](#).

For each AE recorded in the AE section of the eCRF, the physician will assess seriousness (see [Section 8.1.1.2](#)), severity (see [Appendix 4.1](#)), and causality (see [Appendix 4.2](#)).

8.1.2.1 Adverse Event Reporting Period

Qualified HCPs will seek information on AEs at each patient contact. All AEs subject to the collecting and reporting requirements outlined in this protocol, whether reported by the patient or noted by study personnel, will be recorded in the patient's medical record and in the AE section of the eCRF.

Once the patient is enrolled in the study, AEs will be collected from index date (i.e., date of treatment initiation with faricimab) until the end of his or her observation period. After this period, the HCP is not required to actively monitor patients for AEs; but if the treating HCP becomes aware of any related AEs to any medicinal product, they should be notified to the competent authority in the Member State where the reactions occurred or to the MAH of the suspected medicinal product, but not to both (to avoid duplicate reporting).

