Anonymized data will be shared with the medical and scientific community to foster research and support evidence generation. The data elements collected will address different types of research questions through registry-based studies such as secondary data use (SDU) studies.

Start Date of Study

Patient enrollment will be initiated at each site, upon approval from regulatory authorities and IRBs/ ECs, as per local regulation and site agreement implementation and approval of faricimab treatment in nAMD and/or DME according to local labeling. The study start date will be the date of the first patient enrolled.

Study Duration

The expected duration of the study is up to 4 years, depending on the enrollment period duration. This includes approximately 1 to 2 years of recruitment and 2 years for follow-up of every patient (unless the patient discontinues early from the study).

Faricimab—F. Hoffmann-La Roche Ltd

Protocol MR45586, Version 1.0

Baseline Date and Index Date

Baseline is defined as the date when a patient initiates treatment with faricimab in at least one eye (first eye in case of both eyes being treated).

Index date is defined as the date when treatment is initiated at the eye-level. If both eyes are treated with faricimab and the treatment start dates are different, each start date will be used as the index date for the respective eye.

Enrollment Date

Enrollment date is the date the patient signs the Informed Consent Form to participate in this study.

Enrollment date cannot occur earlier than index/baseline date.

End of Study

The study ends when all participants have either completed at least 2 years of follow-up or have ended their participation in the study due to death, withdrawal of consent, participation in an investigational ophthalmology clinical trial, early termination of the study, or discontinuation of the study site, whichever occurs first.

The end of the study date will be the date on which the last information pertaining to the last included patient is recorded in the database.

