6.2 POPULATION

The main patient population for this study, that is new users of faricimab (initiated treatment at enrollment or within 3 months prior to enrollment) in nAMD or DME in at least one eye, has been chosen to allow the capture of the baseline information as it will coincide around the time of study enrollment.

The study will recruit patients who are naïve to anti-VEGF intravitreal therapy in the study eye and those who have previously been treated with anti-VEGF intravitreal therapy in the study eye. Overall, study participation of patients previously treated with intravitreal anti-VEGF will be capped at a maximum of approximately 60% in each

indication. Expected proportion of nAMD and DME patients in the study population is 70% and 30%, respectively.

Patients must meet the following criteria for study entry:

1. Adult patients (≥ 18 years), who have provided signed informed consent, as required per local regulations.
2. Patients, as defined by local regulations and local faricimab product label, who are initiating treatment with faricimab at time of enrollment or have initiated treatment with faricimab within 3 months prior to patient enrollment, in DME or nAMD in at least one eye according to the investigator's discretion in routine clinical practice for anti-VEGF treatment naïve and pre-treated patients.
3. Patients have received at least one faricimab treatment (the first dose) in the study eye.

Patients who meet any of the following criteria will be excluded from study entry:

1. Concomitant participation of the patient in any investigational ophthalmology clinical trial that includes receipt of any ophthalmological investigational drug or procedure within the last 28 days prior to enrollment
2. Current participation in any interventional clinical study
3. Active ocular inflammation and/or suspected/active ocular infection in either eye
4. Patients in whom the study eye has been treated with faricimab for more than 3 months prior to enrollment
5. Patients treated with faricimab who have and are currently participating in patient support programs (PSP) that are Market Research and Patient Support Programs (MAP) including Post Trial Access Programs (PTAP) and Compassionate Use Programs (CUP)
6. Patients with non-ocular sight threatening disease which have an effect on primary endpoint (VA), e.g.: apoplexia
7. Hypersensitivity to the active substance or any of the excipients of Vabysmo (as per label)

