Cumulative time spent in each treatment regimen (i.e., Fixed regimen, T&E, PRN, Other), per nAMD and DME, and per treatment naïve and pre-treated sub-cohorts will be summarized descriptively using mean, median, SD, first quartile, third quartile, minimum, and maximum.

The number and percentage of eyes obtaining treatment intervals of Q8W, Q12W, Q16W and other at 12 months and 24 months will be calculated and summarized by study cohort and for treatment naïve and pre-treated patients (by pre-treatment type).

The number and percentage of eyes discontinuing faricimab treatment in each cohort will be calculated at months 3, 6, 12, and 24 (the reason for treatment discontinuation will be reported at the same time periods).

The number and percentage of eyes switching treatment regimen or treatment type and reason for switch at months 3, 6, 12 and 24 will be calculated and summarized per nAMD and DME.

Time to first treatment switch will be calculated per nAMD and DME and summarized using Kaplan-Meier estimate.

Number and percentage of eyes switched from faricimab to a non-faricimab product will be calculated and summarized at index date, months 3, 6, 12 and 24.

Number, type and frequency of ocular concomitant and subsequent medications received during the study period will be calculated and summarized descriptively by eye.

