6.7.3 Safety Analyses

The Safety Population will consist of all consented patients who receive faricimab in nAMD and DME. Summary tables and listings will be based on the Safety Population (SAS-EL or SAS-PL).

The Safety Endpoint is the incidence of ocular and non-ocular AEs.

Non-ocular AEs/serious adverse events (SAEs) will be assessed at patient-level, per cohort and per sub-cohort, for the SAS-PL.

Ocular AEs/SAEs will be assessed at eye-level, per faricimab and any other anti-VEGF treatment, per cohort (nAMD, DME) and per sub-cohort (treatment naïve and pre-treated eyes), for the SAS-EL.

The incidence of AEs/SAEs will be summarized descriptively by Medical Dictionary for Regulatory Activities (MedDRA) Primary System Organ Class (SOC) and Preferred Term (PT). Cumulative incidence and rates per 100 patient-years or 100 patient-eye years (for eye-level events) (or per 1,000 patient-years, etc., as appropriate) of AEs and SAEs will be calculated.

The number and percentages of patients (or eyes) experiencing AEs and SAEs as well as the number of events will be displayed by SOC, PT, and by severity. AE outcome and duration of AE will be summarized descriptively. For all outcome measures, events with onset through end of study will be summarized at the final analysis.

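### Active ocular inflammation or infection excludes a patient at entry, up to 3 months after the first injection, so part of this adverse-event class drops out of the safety data

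*Protocol*

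**What the plan says.** The start of safety collection is fixed in protocol section 8.1.2.1: "Once the patient is enrolled in the study, AEs will be collected from index date (i.e., date of treatment initiation with faricimab". Section 6.1.1 orders the two dates: "Enrollment date cannot occur earlier than index/baseline date". Section 6.2 admits patients who "have initiated treatment with faricimab within 3 months prior to patient enrollment", and inclusion 3 requires that "Patients have received at least one faricimab treatment (the first dose) in the study eye". Every patient is thus exposed on or before the day of entry.

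Among the criteria that bar study entry, section 6.2 lists exclusion 3, "Active ocular inflammation and/or suspected/active ocular infection in either eye", and exclusion 7, "Hypersensitivity to the active substance or any of the excipients of Vabysmo (as per label". Neither says how to treat a condition that began after the first faricimab injection.

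Section 6.7.1.1 restricts both safety sets, patient-level and eye-level, to patients who meet every inclusion and no exclusion criterion. Section 6.7.3 describes the safety population more widely, as all consented patients receiving faricimab. It names the output: "Cumulative incidence and rates per 100 patient-years or 100 patient-eye years (for eye-level events" and onward. Section 8.1.1.2.2 makes events with severe intraocular inflammation, endophthalmitis among the examples, ocular adverse events of special interest. Section 7.2 and Appendix 2 require consent before any data are documented, and Appendix 2 starts the prospective period the day after enrolment.

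**The concern.** One condition is both a safety outcome and a bar to entering the group in which that outcome is counted. If an eye becomes inflamed or infected after the first injection and is still so when enrolment is considered, the patient is ineligible and the event is never recorded. If the patient is enrolled anyway, section 6.7.1.1 removes the patient from the safety sets. A hypersensitivity reaction to the first injection works the same way through exclusion 7. A patient who dies or leaves the site before consent is also lost.

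The window matters. Appendix 5 describes four monthly initiation doses for faricimab, so a 3-month lag can span most of the initiation phase. Section 6.2.1 names better recording of safety data as an important objective, and the study would understate the early frequency of one of its own special-interest events. The SAP cannot repair this, because eligibility and consent determine who has data at all.

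**Working it through.** The protocol gives no adverse-event rate, no distribution of the lag from index to enrolment and no duration of inflammation. There is therefore no stated figure to reproduce, and what follows is an illustration.

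**Inputs from the protocol**
- The lag L from first injection to enrolment is 0 to 3 months and never negative (6.1.1, 6.2).
- Events are collected from the first injection (8.1.2.1).
- Inflammation or infection active at entry excludes the patient (6.2), and excluded patients are outside the safety sets (6.7.1.1).

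**Assumptions**
- The true 3-month risk of a first inflammation event is 1%, with constant hazard over those 3 months.
- An event at time t stays active for D months.
- The lag is zero, uniform over 0 to 3 months, or 3 months for everyone.
- A patient with active inflammation at time L is not approached again later.

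**Rule.** The event is lost if t < L < t + D. An event that resolves before L is kept, because collection reaches back to index.

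**Uniform lag.** For a rare event, t is close to uniform over 0 to 3 months, so the share of first-3-month events lost is (3D − D²/2)/9 for D up to 3.
- D = 0.5: (1.5 − 0.125)/9 = 0.15, so 0.85 is observed.
- D = 1: (3 − 0.5)/9 = 0.28, so 0.72 is observed.
- D = 2: (6 − 2)/9 = 0.44, so 0.56 is observed.
- D = 3 or more: (9 − 4.5)/9 = 0.50, so 0.50 is observed.

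**Lag of 3 months for all.** The share lost is D/3, which leaves 0.83, 0.67, 0.33 and 0.

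A simulation of 4 million eyes agrees:

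| Time active | No lag | Lag uniform 0–3 months | Lag 3 months for all |
|---|---|---|---|
| 0.5 month | 1.00 | 0.85 | 0.83–0.84 |
| 1 month | 1.00 | 0.72 | 0.67 |
| 2 months | 1.00 | 0.56 | 0.34 |
| persistent | 1.00 | 0.50–0.51 | 0.00 |

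Entries are observed divided by true 3-month risk. A range covers the two late-risk scenarios below.

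**Rate over 24 months.** The dilution is smaller. Across the positive-lag scenarios the ratio is 0.87 to 0.98 with constant hazard. It is 0.67 to 0.95 if the risk after month 3 falls to 0.3% per 3 months.

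**Mixture.** Same-day enrollees lose nothing. If half of patients enrol on the index date (an assumption), the uniform-lag range becomes 0.5 × 1 + 0.5 × 0.85 = 0.92 down to 0.5 × 1 + 0.5 × 0.50 = 0.75.

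**The case against.** Most early adverse events bar nobody from entry. Section 8.1.2.1 collects back to the index date, so an event that has resolved by consent is recorded. Sections 6.1.1 and 6.5.2 keep patients in the study after they stop or switch faricimab. Section 6.2.1 focuses on eyes starting treatment at the time of enrolment, so the lag may often be short. A patient whose inflammation settles inside the 3-month window might still be enrolled afterwards. The study is descriptive, without a comparator, and section 6.9 already concedes that enrollees may be relatively healthier. All of this stands, and it limits the point to one class of ocular event, hypersensitivity, and early death or loss to the site. It does not remove the point: section 6.9 treats healthier enrollees as a matter of representativeness and does not mention exclusion on an event that follows exposure.

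A reader might infer three stronger things that the documents do not support.
- **All adverse-event rates are biased low.** The entry criteria select only on the conditions named above.
- **The Kaplan-Meier curves carry immortal time.** Section 6.7.2.2 says "Time to first treatment switch will be calculated per nAMD and DME and summarized using Kaplan-Meier estimate", and section 6.7.4 times the 70-letter threshold from index. Neither a switch nor a 70-letter reading prevents enrolment, and treatment and visual acuity data are collected from index. A claim that early non-responders are under-enrolled, flattering the visual acuity result, has no supporting text either.
- **The person-time denominator is wrong.** Section 6.7.3 does not say where it starts. That may be set in the SAP, which is not at hand, and a later start would not bring the excluded events back.

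**Conclusion.** The point holds in this limited form and should be fixed. Sections 6.2, 6.7.1.1 and 8.1.2.1 together remove inflammation or infection that follows the first injection and is still active at entry, among patients enrolled after their index date. Post-injection hypersensitivity, early death and loss to the site are removed too. Events resolved before enrolment, same-day enrollees and second eyes first injected after enrolment are unaffected.

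The direction is downward whenever there is a lag; the size is not known. Under the uniform lag, the observed 3-month risk of this event class lies between about 0.85 of the truth (active half a month) and about 0.5 (persistent). The 0.5 must not be read as a general halving of early adverse-event rates. It needs both the assumed lag and inflammation that never clears before entry.

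**What to change.** 1. In section 6.2 and the synopsis, state that exclusions 3 and 7 refer to the patient's status before the first faricimab injection. Onset after it then removes nobody from enrolment or, through section 6.7.1.1, from the safety sets. This concerns entry to data collection only and leaves treatment to the physician. Bring the safety population in section 6.7.3 into line with section 6.7.1.1.
2. Keep a log of patients not enrolled because of inflammation or infection that arose after the first injection.
3. Report early ocular adverse events separately for patients enrolled on the index date and for those enrolled later.
4. Use delayed entry at enrolment only as a sensitivity analysis. It drops validly recorded early events. With a uniform lag over 91 days, the average share under observation in the first week is 3.5/91 = 3.8%, about 33 of 850 patients.
5. Name this selection in section 6.9.

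The cost is a short amendment, a small log and one extra table. Early deaths and patients lost before consent remain uncounted, which is why item 5 is needed as well.

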8.1.2.2 Procedures for Recording Adverse Events

HCPs should use correct medical terminology/concepts and MedDRA coding when recording AEs in the AE section of the eCRF. Colloquialisms and abbreviations should be avoided.

See [Appendix 4](#) for further specific instructions regarding:

- IVT-related reactions
- Diagnosis versus signs and symptoms
- AEs occurring secondary to other AEs
- Persistent or recurrent AEs
- Abnormal laboratory values
- Abnormal vital sign values
- Abnormal liver function tests
- Deaths
 - All events with an outcome or consequence of death should be classified as SAEs and reported to the MAH immediately. In certain circumstances, however, suspected adverse reactions with fatal outcome may not be subject to expedited reporting (see [Section 8.3](#)). All deaths that occur during the

protocol-specified AE reporting period, regardless of relationship to study medicine, must be recorded in the AE section of the eCRF and be immediately reported to the MAH

- Pre-existing medical conditions
- Lack of therapeutic efficacy
- Hospitalization or prolonged hospitalization
- Overdoses, misuses, abuses, off-label use, occupational exposure, or medication error
- Quality defects, falsified medicinal products and product complaints
- Drug interactions

8.1.3 Reporting Requirements from Healthcare Professional to Marketing Authorization Holder

8.1.3.1 Immediate Reporting Requirements from Healthcare Professional to Marketing Authorization Holder

Certain events require immediate reporting to allow the MAH and the regulatory authorities to take appropriate measures to address potential new risks associated with the use of the medicine. The HCP must report such events to the MAH immediately; under no circumstances should reporting take place more than 24 hours after the HCP learns of the event. The following is a list of events that the HCP must report to the MAH within 24 hours after learning of the event, regardless of relationship to study medicine:

- SAEs
- Non-serious AESI
- Pregnancies

The HCP must report new significant follow-up information for these events to the MAH immediately (i.e., no more than 24 hours after becoming aware of the information). New significant information includes the following:

- New signs or symptoms or a change in the diagnosis
- Significant new diagnostic test results
- Change in causality based on new information
- Change in the event's outcome, including recovery
- Additional narrative information on the clinical course of the event

For reports of SAEs and AESI, including follow-up, HCPs should record all case details that can be gathered immediately (i.e., within 24 hours) in the AE page of the eCRF and submit the report via the EDC system. A report will be generated and sent to Roche Drug Safety by the EDC system.

In the event that the EDC system is temporarily unavailable, please refer to [Section 8.1.3.3](#).

HCPs must also comply with local requirements for reporting SAEs to the local health authority and IRB/EC.

8.1.3.2 Reporting Requirements for Non-Serious Adverse Events

For all non-serious AEs, including follow-up reports, HCPs must record all case details that can be gathered within 30 calendar days of learning of the event on the AE section of the eCRF and submit the report via the EDC system. A report will be generated and sent to Roche Drug Safety to allow appropriate reporting to relevant competent authorities.

In the event that the EDC system is temporarily unavailable, please refer to [Section 8.1.3.3](#).

8.1.3.3 If EDC System is Temporarily Unavailable

In the event that the EDC system is temporarily unavailable, a completed paper reporting form and fax coversheet should be faxed/scanned to Roche Drug Safety or its designee immediately (i.e., no more than 24 hours after learning of the event) or within 30 calendar days for non-serious AEs if not AESI, using the fax number or email address provided to treating physicians.

Once the system is available again, all information should additionally be entered and submitted via the EDC system.

8.1.3.4 Reporting Requirements for Pregnancies/Breastfeeding

8.1.3.4.1 Pregnancies/Breastfeeding in Female Patients

Female patients of childbearing potential will be instructed to immediately inform the physician if they become pregnant during the study or within 28 days after the last intravitreal injection. A Pregnancy Report should be completed by the physician immediately (i.e., no more than 24 hours after learning of the pregnancy) and sent to Roche Drug Safety. Pregnancy should not be recorded in the AE eCRF. The treating physician should discontinue the medicinal product and counsel the patient, discussing the risks of the pregnancy and the possible effects on the fetus. Monitoring of the patient should continue until the conclusion of the pregnancy. Any SAEs associated with the pregnancy (e.g., an event in the fetus, an event in the mother during or after the pregnancy, or a congenital anomaly/birth defect in the child) should be reported on the AE section of the eCRF. In addition, the treating physician will submit a Clinical Trial Pregnancy Reporting Form when updated information on the course and outcome of the pregnancy becomes available.

Suspected adverse reactions that occur in infants following exposure to a medicinal product from breast milk should be reported to Roche Drug Safety.

8.1.3.4.2 Pregnancies in Female Partners of Male Patients

Not applicable for this study.

8.1.3.4.3 Abortions

Any abortion should be classified as an SAE (as the MAH considers abortions to be medically significant), recorded in the AE section of the eCRF, and reported to the MAH immediately (i.e., no more than 24 hours after learning of the event; see [Section 8.1.3.1](#)).

If a therapeutic or elective abortion was performed because of an underlying maternal or embryofetal toxicity, the toxicity should be classified as an SAE, recorded on the adverse event eCRF, and reported to the MAH immediately (i.e., no more than 24 hours after learning of the event). A therapeutic or elective abortion performed for reasons other than an underlying maternal or embryofetal toxicity is not considered an AE.

All abortions should be reported as pregnancy outcomes on the paper Pregnancy Reporting Form.

